14.2 EFFICACY DATA

Primary efficacy analysis

Table	Title	Pop	Top.Line
14.2.1.1	Percentage of patients with anterior chamber cell grade of "0" compared to placebo at Day 8	FAS	X
14.2.1.2	Percentage of patients with anterior chamber cell grade of "0" compared to placebo at Day 8	PP at Visit 3	
14.2.1.3	Percentage of patients with anterior chamber cell grade of "0" compared to placebo at Day 8	FAS non- RM	Х

Sponsor: Laboratorios Salvat, S.A. Study Code: CLOBOF3-16IA01 NCT No.: NCT04246801

Main Secondary efficacy analysis

Table	Title	Pop	Top.Line
14.2.2.1	Proportion of patients with VAS pain score of "0" (no eye pain) compared to placebo at Day 8.	FAS	Х
14.2.2.2	Proportion of patients with VAS pain score of "0" (no eye pain) compared to placebo at Day 8.	PP at Visit 3	
14.2.2.3	Proportion of patients with VAS pain score of "0" (no eye pain) compared to placebo at Day 8.	FAS non- RM	X

Secondary efficacy analysis

Table	Title	Pop	Top.Line
14.2.3.1	Proportion of patients with anterior chamber cell grade of "0" compared to placebo at Day 3, Day 15 and Day 29	FAS non- RM	X
14.2.3.2	Proportion of patients with anterior chamber cell grade of "0" compared to placebo at Day 3, Day 15 and Day 29	FAS	
14.2.3.3	Proportion of patients with VAS pain score of "0" (no eye pain) compared to placebo at Day 3, Day 15 and Day 29.	FAS non- RM	X
14.2.3.4	Proportion of patients with VAS pain of "0" compared to placebo at Day 3, Day 15 and Day 29.	FAS	
14.2.4.1	Change from Baseline to Day 3, Day 8, Day 15 and Day 29 compared to placebo in the proportion of patients with different anterior chamber cell grades. Improvement and no Improvement table.	FAS non- RM	
14.2.4.2	Change from Baseline to Day 3, Day 8, Day 15 and Day 29 compared to placebo in the proportion of patients with different anterior chamber cell grades. Descriptive table	FAS non- RM	
14.2.5.1	Change from Baseline to Day 3, Day 8, Day 15 and Day 29 compared to placebo in the proportion of patients with different anterior chamber flare grades. Improvement and no Improvement table.	FAS non- RM	
14.2.5.2	Change from Baseline to Day 3, Day 8, Day 15 and Day 29 compared to placebo in the proportion of patients with different anterior chamber flare grades. Descriptive table	FAS non- RM	
14.2.6.	Proportion of patients with anterior chamber cell grade of "≤0.5+" and flare grade of "0" compared to placebo at Day 3, Day 8, Day 15 and Day 29.	FAS non- RM	
14.2.7.	Proportion of patients with anterior chamber cell grade of "≤1+" compared to placebo at Day 3, Day 8, Day 15 and Day 29.	FAS non- RM	

Sponsor: Laboratorios Salvat, S.A. Study Code: CLOBOF3-16IA01 NCT No.: NCT04246801

14.2.8.	Proportion of patients with anterior chamber cell grade of "0" and flare grade of "0" compared to placebo at Day 3, Day 8, Day 15 and Day 29.	FAS non- RM
14.2.9.1	Frequency of chemosis (yes/no) compared to placebo at Baseline, Day 3, Day 8, Day 15 and Day 29.	FAS non- RM
14.2.9.2	Frequency of bulbar conjunctival injection (yes/no) compared to placebo at Baseline, Day 3, Day 8, Day 15 and Day 29.	FAS non- RM
14.2.9.3	Frequency of ciliary injection (yes/no) compared to placebo at Baseline, Day 3, Day 8, Day 15 and Day 29.	FAS non- RM
14.2.9.4	Frequency of corneal edema (yes/no) compared to placebo at Baseline, Day 3, Day 8, Day 15 and Day 29.	FAS non- RM
14.2.9.5	Frequency of keratic precipitates (yes/no) compared to placebo at Baseline, Day 3, Day 8, Day 15 and Day 29.	FAS non- RM
14.2.10.1	Change from Baseline to Day 3, Day 8, Day 15 and Day 29 compared to placebo in the proportion of patients with chemosis (yes/no)	FAS non- RM
14.2.10.2	Change from Baseline to Day 3, Day 8, Day 15 and Day 29 compared to placebo in the proportion of patients with bulbar conjunctival injection (yes/no)	FAS non- RM
14.2.10.3	Change from Baseline to Day 3, Day 8, Day 15 and Day 29 compared to placebo in the proportion of patients with ciliary injection (yes/no)	FAS non- RM
14.2.10.4	Change from Baseline to Day 3, Day 8, Day 15 and Day 29 compared to placebo in the proportion of patients with corneal edema (yes/no)	FAS non- RM
14.2.10.5	Change from Baseline to Day 3, Day 8, Day 15 and Day 29 compared to placebo in the proportion of patients with keratic precipitates (yes/no)	FAS non- RM
14.2.11.1	Change from Baseline to Day 3, Day 8, Day 15 and Day 29 compared to placebo in the severity of chemosis. Improvement or no Improvement.	FAS non- RM
14.2.11.2	Change from Baseline to Day 3, Day 8, Day 15 and Day 29 compared to placebo in the severity of chemosis. Descriptive table	FAS non- RM
14.2.11.3	Change from Baseline to Day 3, Day 8, Day 15 and Day 29 compared to placebo in the severity of bulbar conjunctival injection. Improvement or no Improvement.	FAS non- RM
14.2.11.4	Change from Baseline to Day 3, Day 8, Day 15 and Day 29 compared to placebo in the severity of bulbar conjunctival injection. Descriptive table	FAS non- RM

Improvement

14.2.15.2

14.2.16.1

14.2.16.2

14.2.17

Sponsor: Laboratorios Salvat, S.A. Study Code: CLOBOF3-16IA01 NCT No.: NCT04246801

14.2.11.5	Change from Baseline to Day 3, Day 8, Day 15 and Day 29 compared to placebo in the severity of ciliary injection. Improvement or no Improvement	FAS non- RM	
14.2.11.6	Change from Baseline to Day 3, Day 8, Day 15 and Day 29 compared to placebo in the severity of ciliary injection. Descriptive table	FAS non- RM	
14.2.11.7	Change from Baseline to Day 3, Day 8, Day 15 and Day 29 compared to placebo in the severity of corneal edema. Improvement or no Improvement.	FAS non- RM	
14.2.11.8	Change from Baseline to Day 3, Day 8, Day 15 and Day 29 compared to placebo in the severity of corneal edema. Descriptive table	FAS non- RM	
14.2.11.9	Change from Baseline to Day 3, Day 8, Day 15 and Day 29 compared to placebo in the severity of keratic precipitates. Improvement or no Improvement	FAS non- RM	
14.2.11.10	Change from Baseline to Day 3, Day 8, Day 15 and Day 29 compared to placebo in the severity of keratic precipitates. Descriptive table	FAS non- RM	
14.2.12	MMRM. Change from Baseline to Day 3, Day 8, Day 15 and Day 29 compared to placebo in the visual analog scale (VAS) photophobia score.	FAS non- RM	
14.2.13	MMRM. Change from Baseline to Day 8, Day 15 and Day 29 compared to placebo in Snellen best.corrected visual acuity (BCVA) score.	FAS non- RM	
14.2.14	MMRM. Change from Baseline to Day 3, Day 8, Day 15 and Day 29 compared to placebo in the VAS pain score.	FAS non- RM	X
14.2.15.1	Change from baseline to Day 3, Day 8, Day 15 and Day 29	FAS	

Sponsor: Laboratorios Salvat, S.A. Study Code: CLOBOF3-16IA01 NCT No.: NCT04246801

14.2.18	Percentage of patients with anterior chamber cell grade of "0" compared to placebo at Day 8. Sensitivity Analysis	FAS non- RM	
14.2.19.1	Proportion of patients with VAS pain score of "0-0.2 cm" (no eye pain) compared to placebo at Day 3, Day 8, Day 15 and Day 29 (FAS non-RM set).	FAS non- RM	X
14.2.19.2	Proportion of patients with VAS pain score of "0-0.2 cm" (no eye pain) compared to placebo at Day 3, Day 8, Day 15 and Day 29 (FAS Set).	FAS	X
14.2.20.1	Proportion of patients with VAS pain score of "0-0.4 cm" (no eye pain) compared to placebo at Day 3, Day 8, Day 15 and Day 29 (FAS non-RM set).	FAS non- RM	X
14.2.20.2	Proportion of patients with VAS pain score of "0-0.4 cm" (no eye pain) compared to placebo at Day 3, Day 8, Day 15 and Day 29 (FAS Set).	FAS	X

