Pain after ophthalmic surgery may be considered a sign of a possible complication. Severe pain is assumed to be a sign of postoperative inflammation or infection, making it a concern for both patient and physician. However, a surgery without perioperative complications may also be associated with significant postoperative pain during the early recovery. Thus, appropriate counseling and pain management should be provided to improve quality of life (6).

Also, uncontrolled inflammation may lead to serious side effects, such as posterior synechia, uveitis, cystoid macular edema or secondary glaucoma. Management of inflammation is thus a mainstay in modern cataract surgery (8). Despite surgical advances, post-cataract surgery inflammation is still a common cause of patient discomfort, delayed recovery and reduced visual outcome (9).

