2.3 Risk-Benefit Assessment

Benefits

Clobetasol is a synthetic fluorinated corticosteroid. The corticosteroids constitute a class of primarily synthetic steroids used topically as anti-inflammatory and antipruritic agents. Older corticosteroids have been used since the 1950's, while new molecules were more recently developed and have been proven effective in controlled clinical trials.

Ophthalmic corticosteroids have a very well-known effect by decreasing the number and function of inflammatory cells, vascular permeability, and by inhibiting chemical mediators of inflammation, thus it could be considered that corticosteroids have a class effect for their indications in post-surgical inflammation.

Particularly, clobetasol propionate has been approved for the treatment of other inflammatory topical processes for over 30 years (Temovate® Cream) showing a positive benefit-risk profile as its efficacy is widely demonstrated with a good safety profile. Moreover, the use of corticosteroids for short-term treatment of local inflammation, usually in the anterior segment of the eye (including inflammation post-surgery) is widely supported in the literature.

Risks

It is known that exogenous corticosteroids can cause hypertension and other cardiovascular adverse effects including a hypercoagulability state and dyslipidemia. However, these adverse effects are linked to long-term systemic exposure to corticosteroids.

Ocular administration of clobetasol propionate and other corticosteroids have been linked to rare ocular adverse events (AEs) such as IOP elevation, cataracts, ocular hypertension, glaucoma or inhibition of wound healing. The limited exposure planned for this study (one drop QID/14 days) aims to prevent these rare AEs.

Benefit-Risk Assessment

Topical corticosteroids are safer than systemic glucocorticoids due to the lower systemic exposure. Furthermore, ocular administration results in even lower systemic exposure, below

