9.1.1 Sample Size

A two group $\chi 2$ test with a 0.05 two-sided significance level will have 80% power to detect the difference between a proportion with complete resolution of anterior chamber cells in the active group of 0.22 and the placebo group proportion of 0.07 (odds ratio of 3.747) when the sample size is 202. Considering a 4% lost to follow-up rate a final sample size of 210 patients will be required (140 clobetasol, 70 placebo, in a 2:1 randomization ratio).

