5 DATA SETS TO BE ANALYSED

The following analysis sets will be used for the statistical analysis and presentation of data:

• Full Analysis Set (FAS): The FAS will be the primary analysis set for the efficacy endpoints and will include all randomized patients. The FAS population will be analyzed according to the planned treatment (rather than treatment actually received).

Statistical Analysis Plan Sponsor: Laboratorios Salvat. S.A. Version: Final 3 Study Code: CLOBOF3-16IA01 Date: 09-JUL-2021

NCT No.: NCT04246801

Full Analysis Set without including rescued subjects (FAS non-RM set): The FAS non-RM will be the analysis set for the efficacy endpoints and will include all randomized patients without including rescued subjects (prohibited medication allowed.

- Safety Analysis (SAF) set The safety set will be the primary analysis set for the safety endpoints and will include all randomized patients who instilled at least one dose of IMP or placebo. The SAF will be analyzed according to the treatment actually received.
- Per Protocol (PP) Population: The PP population set will be tested to confirm the robustness of the efficacy analyses and will include all patients in the FAS who have no major protocol deviations (i.e. patients who comply the protocol sufficiently to ensure that the data exhibits the effects of the IMP or placebo when administered as intended). Protocol violations include: violations of entry criteria, lack of compliance and the use of prohibited medication. The PP population will be analyzed according to the treatment actually received.

Lack of compliance is defined as less than 80% compliance (section 6.3.8).

Efficacy analyses will be based on both the FAS and the PP, but the FAS will be considered the primary analysis population.

Safety analyses will be based on the SAF.

Primary efficacy and key secondary efficacy analysis will be performed for all efficacy endpoints, analyzing:

-all subjects who were randomized (i.e., FAS set),

AND

-all subjects who were randomized without including rescued subjects (i.e., FAS non-RM set)

Secondary efficacy analysis will be performed analyzing all subjects included in the FAS non-RM populations, hereinbefore described.

Sensitivity analysis described in the section 6.3.7 will be performed analyzing all subjects included in FAS set populations, hereinbefore described.

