6.3 Hypotheses and Statistical Methods

6.3.1 Definitions

Baseline	(Visit 1 (Day 1, 24 h after the cataract surgery).				
Time calculation	Differences between dates to express duration will be calculated as the final date - initial date + 1. To convert these days differences to other units, the following conversion factors will be used: 1 year = 365.25 days and 1 month = 30.4375 days.				
	Ex. Age = (informed consent date – date of birth + 1) / 365.25				
Absolute change	Absolute change from Baseline at Visit X will be calculated as:				
from Baseline	Absolute change from Baseline = Visit X - Baseline				
Percentage change	Percentage change from Baseline at Visit X will be calculated as:				
from Baseline	Percentage change from Baseline [%] = ((Visit X - Baseline)/Baseline) *100				
	In case of Baseline = 0 no percentage change from baseline will be calculated.				
Signs of ocular inflammation (yes/no)	The presence/absence of the different signs of ocular inflammation: Chemosis, Bulbar conjunctival injection, ciliary injection, corneal edema, keratic precipitates will be defined as:				
	No: grade=0 (absence)				
	Yes: grade=1, 2 or 3 (presence)				
Conversion Snellen	Step 1. Mar = Snellen Denominator/Snellen Numerator				
to LogMar	Step 2. LogMar = log (Mar)				
	Example: Snellen 20/40				
	Mar = 40/20 = 2				
	LogMar= log(2) = 0.3				
Treatment Emergent Adverse Event	Treatment Emergent Adverse Events (TEAEs) are defined as an event that emerges during treatment having been absent pretreatment or worsens relative to the pre-treatment state:				
	First dose IMP/Pacebo date ≤ start date AE ≤ last dose IMP/Placebo date				
Rescue medication	The following prohibited medications will be considered as rescue medication when administered to subjects not responding to IMP or placebo:				
	 Any systemic or local therapy with corticosteroids (other than the study drug) or immunosuppressant (except pre- surgical and/or surgical administration of 1 drop of a topical NSAID or corticosteroid, at the investigator discretion) 				

Date: 09-JUL-2021

Sponsor: Laboratorios Salvat, S.A. Study Code: CLOBOF3-16IA01

NCT No.: NCT04246801

	 Any topical ocular medication (except preservative-free antibiotics for prophylactic purposes and preservative-free artificial tears) Any systemic NSAID or opioids drugs (except occasional use of OTC formulations titrated no more than one single dose per week) 			

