16.2.2.1	Protocol Deviations	ALL	
16.2.3.1	Patients excluded from SAF	ALL	
16.2.3.2	Patients excluded from FAS	ALL	
16.2.3.3	Patients excluded from PP	ALL	

Demographic and baseline characteristics

Listing	Title	Pop	Top.Line
16.2.4.1	Demographic data	SAF	
16.2.4.2	Relevant Medical History	SAF	
16.2.4.4	Urine Pregnancy test	SAF	
16.2.4.5	Cataract diagnosis	SAF	
16.2.4.5	Inclusion Criteria Not Met and Exclusion Criteria Met	SAF	

Compliance

Listing	Title	Pop	Top.Line
16.2.5	Compliance with IMP/Placebo	SAF	

Efficacy data

Listing	Title	Pop	Top.Line
16.2.6.1	Slit Slamp Examination	SAF	
16.2.6.2	BCVA by Snellen chart	SAF	
16.2.6.3	Eye pain (VAS)	SAF	
16.2.6.4	Eye discomfort	SAF	
16.2.6.5	Photophobia	SAF	

Sponsor: Laboratorios Salvat, S.A. Study Code: CLOBOF3-16IA01

NCT No.: NCT04246801

16.2.6.6	Indirect ophthalmoscopy	SAF	
----------	-------------------------	-----	--

Adverse Events

Listing	Title	Pop	Top.Line
16.2.7.1	Adverse Events	SAF	

Other Safety assessments

Listing	Title	Pop	Top.Line
16.2.9	Vital signs	SAF	
16.2.10.1	Physical examination	SAF	
16.2.10.2	Eye examination	SAF	
16.2.11	IOP measurementsby Goldman Tonometer	SAF	

Concomitant medication

Listing	Title	Pop	Top.Line
16.2.12.1	Prior Medications and Therapies tabulated by ATC level 3 group and WHO preferred name	SAF	
16.2.12.2	All Concomitant Medications and Therapies tabulated by ATC level 3 group and WHO preferred name	SAF	
16.2.12.3	Rescue and prohibited Concomitant Medications tabulated by ATC level 3 group and WHO preferred name	SAF

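### Visual acuity has one table, an efficacy mean-change model from the Day 1 post-operative baseline; no safety-set table counts, by arm, the eyes with a defined loss of acuity

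*SAP*

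**What the plan says.** **Where acuity sits.** Protocol 7.3 and SAP 3.2 make change in BCVA a secondary efficacy endpoint. Neither safety endpoint list (protocol 7.4, SAP 3.3) names it. The eye examination described in SAP 6.3.11 covers pupils, alignment and motility, confrontation fields and anterior vitreous, at Screening and Early Termination only. Protocol Table 1 schedules BCVA at Screening, Visits 1, 3, 4 and 5, and Early Termination.

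**What is produced.** The only table is 14.2.13: "MMRM. Change from Baseline to Day 8, Day 15 and Day 29 compared to placebo in Snellen best.corrected visual acuity (BCVA) score". SAP 8.1 adds summary statistics to the MMRM tables. The safety set has one BCVA output, Listing 16.2.6.2 ("BCVA by Snellen chart"), placed under efficacy data in SAP 8.2.

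**Reference point.** SAP 6.3.1 defines baseline as "Visit 1 (Day 1, 24 h after the cataract surgery"). The same section converts Snellen to logMAR.

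**Population.** The output list and SAP section 5 use FAS non-RM, which "will include all randomized patients without including rescued subjects". SAP 6.3.6.2 and protocol 9.1.12 say FAS.

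**Harms the plan names.** Protocol 2.1 warns that "uncontrolled inflammation may lead to serious side effects, such as posterior synechia, uveitis, cystoid macular edema or secondary glaucoma". Protocol 2.3 links ocular corticosteroids to rare events "such as IOP elevation, cataracts, ocular hypertension, glaucoma or inhibition of wound healing".

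**The concern.** Several of the named harms can cost vision, on either arm: steroid complications on active, uncontrolled inflammation on vehicle. The natural safety question is how many study eyes in each arm lost acuity by a stated amount. Three features of the plan keep the report from answering it.

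- Table 14.2.13 summarises average change. A few worsening eyes among many recovering ones hardly move an average.
- As listed, the table drops patients who were rescued, a post-randomisation exclusion that may remove the eyes in most trouble.
- The adverse event tables depend on an investigator reporting the loss. No rule turns a measured BCVA loss into an adverse event, and the visit notes in protocol 4.3.2 exclude expected changes from routine surgery from capture.

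At stake is a descriptive safety result that is basic to a benefit-risk statement for an eye drop. Neither the primary nor the key secondary analysis is affected.

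**Working it through.** **1. The plan's own figure.** The plan gives no figure for acuity. Its sample size supplies the arm sizes used below: "0.05 two-sided significance level will have 80% power to detect the difference", with an "active group of 0.22 and the placebo group proportion of 0.07 (odds ratio of 3.747) when the sample size is 202". A pooled-variance two-group test at 2:1 needs 68 + 136 = 204, and at 202 its power is 80.2%. 202 / 0.96 = 210.4, against the stated 210 (140 and 70). The figure reproduces and has no further bearing here.

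**2. What a mean shows.** Assumptions, because the documents give no values: a fraction f of the 140 active eyes loses 0.3 logMAR, no placebo eye does, and all other eyes change by m.

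Shift in the active mean = f × (0.3 − m).

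| f | m = 0 | m = −0.20 |
|---|---|---|
| 3% | 0.009 | 0.015 |
| 5% | 0.015 | 0.025 |

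95% half-width of the difference = 1.96 × SD × √(1/140 + 1/70) = 1.96 × SD × 0.1464.

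| SD of change (assumed) | Half-width |
|---|---|
| 0.15 | 0.043 |
| 0.20 | 0.057 |
| 0.30 | 0.086 |

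The largest shift (0.025) is below the smallest half-width (0.043).

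**3. What a count shows.** The 5% case would read 7/140 = 5.0% (exact 95% CI 2.0% to 10.0%), against 0/70 (upper limit 5.1%).

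**4. Who is missing under FAS non-RM.** For assumed rescue rates (active vs placebo) of 3% vs 10%, 5% vs 20% and 10% vs 30%, the eyes removed are about 4 vs 7, 7 vs 14 and 14 vs 21.

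**5. The adverse event route.**
- SAP 6.3.1 ends the treatment-emergent window at the last dose. SAP 6.3.10 states no end date but refers back to 6.3.1. The endpoint in SAP 3.3 runs to Day 29.
- With the last dose on Day 14 or 15, 29 − 14 = 15 or 29 − 15 = 14 of the 28 days from Day 1 to Day 29 fall outside the 6.3.1 window.
- Protocol 6.7.2 has rescued patients stop study drug, so under 6.3.1 their window closes then. A loss that starts after rescue would be in neither Table 14.2.13 as listed nor a treatment-emergent table.
- Protocol 9.1.13 foresees tabulating all adverse events. SAP 6.1 says the SAP supersedes the protocol's methods, and the adverse event tables in its 14.3 list cover treatment-emergent events only.

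**The case against.** The strongest reply is that the plan does not ignore acuity loss. Much of that reply stands, and it rules out several stronger readings.

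- **A reader might infer that lost vision is counted in no by-arm safety table.** It is not so. A loss reported as a treatment-emergent event is counted by arm in the safety set, rescued patients included, in Tables 14.3.1.2.1 and 14.3.1.2.2. What is missing is a count based on the measurement.
- **A reader might infer that the MMRM table conceals every loss.** SAP 6.3.2 requires minimum, quartiles and maximum, so the worst single change in each arm at each visit is printed. That is one eye per arm, not a count, and a 5% tail need not move the quartiles.
- **A reader might take exclusion of rescued eyes as settled.** The documents contradict each other on it. On the FAS, that part of the point falls away, but the output is still a mean change.
- **A reader might treat the Screening value as the yardstick of true loss.** It is measured through the cataract, so surgical gain can mask a later loss. Day 1 is the pre-dose reference for the randomised comparison.
- **A reader might call BCVA the only measure of visual harm, or this the first ocular use in humans.** IOP has a by-arm safety table (14.3.4.2), ophthalmoscopy is scheduled at Visits 4 and 5, and confrontation fields are tested at Early Termination. Protocol 2.1.4 says only that the product has had no trials in the proposed indications.

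It is also fair that the counts would be small. Fisher's exact test gives p = 0.30 for 4/140 vs 0/70 and p = 0.098 for 7/140 vs 0/70. The table would be descriptive only.

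**Conclusion.** The point holds in a limited form. As written, the report would have no by-arm safety-set count of eyes with a defined BCVA loss. The one acuity table is an efficacy mean change with summary statistics, from a Day 1 post-operative baseline, on a population that the documents state in two ways. The adverse event tables fill the gap only in part, because reporting is not tied to the measurement and the SAP 6.3.1 window stops at the last dose.

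The size is illustrative. A mean shift of about 0.009 to 0.025 logMAR, against a half-width of 0.043 to 0.086, rests on assumed loss rates of 3% to 5%, an assumed loss of 0.3 logMAR, an assumed change of 0 to −0.20 in the other eyes, and an assumed SD of 0.15 to 0.30. The gap itself does not depend on those values; it follows from the list of outputs. This is an inexpensive improvement to safety reporting, not a flaw in the efficacy conclusions.

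**What to change.** 1. Add one descriptive table by arm on the safety set, including rescued patients and Early Termination readings. Give the number and percentage of study eyes with a pre-defined logMAR worsening (for example at least 0.3) from Visit 1, at Days 8, 15 and 29 and at the worst post-baseline visit. Show change from Screening as a supplementary view only, labelled as measured through the cataract. Keep Table 14.2.13 as the efficacy summary.
2. Reconcile SAP section 5 and the SAP 8.1 output list with SAP 6.3.6.2 and protocol 9.1.12 on the population for Table 14.2.13.
3. Reconcile SAP 3.3, 6.3.1 and 6.3.10 on when the treatment-emergent window ends.

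The cost is SAP wording and one table from data already collected, using the logMAR conversion already in SAP 6.3.1. It needs no new visit, alpha or sample size. The drawback is an extra table with small counts and no inferential use.
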